13.9. Interim Analyses

13.9.1. Interim Analyses

The DSMB will perform unblinded analyses when 75 and 150 participants have completed the 28-day study period. The first DSMB analysis will be for safety and the second will be for safety and review of primary efficacy data for futility.

- a. First Interim Analysis: When 75 participants have completed the 28-day study period a safety analysis report will be prepared by the unblinded study statistician and submitted to the DSMB for review. The DSMB will evaluate potential safety imbalances between the two study groups and consider whether or not safety concerns preclude continuation of the study, or whether some study modification is needed.
- b. Second Interim Analysis: When 150 study participants have completed the 28-day study period the Study and Data Coordinating Center will perform an unblinded summary of safety data and the primary endpoint for the DSMB to review. The safety data will be reviewed for imbalances between the two study groups, as at the first interim analysis. The primary endpoint data will be reviewed to evaluate the rate ratio between the study groups. No matter what the estimated rate ratio is, the study will not be stopped early to declare efficacy.
- c. The biostatisticians at the Study and Data Coordinating Center have conducted extensive simulations to assess this rule under various scenarios. In the simulations, we assume the placebo+SOC arm would have similar recovery experience as shown for the remdesivir arm in Panel C of Figure 2 in the ACTT-1 study (Beigel, et al. 2020). The time to recovery was modeled using the Weibull distribution to describe this experience. The Weibull distribution assumes the hazard decreases over time and we found this distribution with shape parameter 0.73 and median survival of 7 days fit the recovery curve well. For the ic14+SOC arm, the shape parameter is the same as that of the placebo+SOC arm, and the scale parameter is determined by pre-specified recovery rate ratio (RR). Participants are randomized to the placebo+SOC and ic14+SOC arms at a 1:1 ratio. After 150 participants complete 28 days of follow-up, the Cox PH regression will be used to estimate the RR. If the estimated RR is less than a pre-specified threshold, then the DSMB would recommend stopping the trial. Table 6 summarizes the probability of stopping the trial for different values of the threshold and the true underlying RR. In order to achieve a balance between: 1) the need to terminate the trial in the event that the

intervention is actually harmful, and 2) premature termination of the trial if the intervention is actually beneficial. We have selected the stopping rule threshold of 1.0 to have a high probability (>50%) of stopping the trial if the intervention is harmful (i.e. true RR is <1.0) and a low probability (<10%) of stopping the trial if the intervention is beneficial (i.e. true RR is >1.3)(see highlighted row in Table 6).

Table 6. Evaluation of Stopping Rules								
Stopping Threshold	True Recovery Rate Ratio (RR)							
	0.8	0.9	1.0	1.1	1.2	1.3	1.4	1.5
0.96	0.84	0.64	0.41	0.22	0.10	0.040	0.014	0.0054
1.00	0.89	0.71	0.50	0.29	0.15	0.064	0.024	0.0086
1.02	0.91	0.75	0.54	0.33	0.17	0.078	0.032	0.011
1.04	0.92	0.79	0.58	0.37	0.20	0.097	0.041	0.015
1.06	0.94	0.81	0.62	0.42	0.23	0.12	0.052	0.021
1.08	0.95	0.84	0.66	0.46	0.27	0.14	0.065	0.027
1.10	0.96	0.86	0.70	0.50	0.31	0.17	0.080	0.034
1.14	0.98	0.91	0.76	0.58	0.38	0.22	0.12	0.054

The values in the table show the probabilities for stopping the trial at given stopping thresholds for different underlying true recovery rate ratios (RR>1 is beneficial).

13.9.2. Interim Analysis of Safety Data

13.9.3. Futility Analysis

13.10. Statistical Hypotheses

The primary hypothesis is that IC14 will be efficacious in treating COVID 19 participants. To test this hypothesis, we will use time to recovery as the primary endpoint. The treatment effect will be presented as the recovery rate ratio. A ratio greater than 1 indicates beneficial effect of IC14. A ratio of 1 corresponds to the null hypothesis that IC14 has no treatment effect compared to placebo.

13.11. Sample Size Calculations

It is assumed that the placebo arm will have a similar recovery experience as shown for the remdesivir arm in Panel C of Figure 2 in the ACTT-1 study (Beigel et al. 2020). The time to recovery can be modeled using the exponential or the Weibull distribution to describe this experience. The exponential distribution assumes constant hazard and the Weibull distribution assumes the hazard decreases with time. The Weibull distribution with shape parameter 0.73 and median time to recovery of 7 days appears to fit the recovery curve better than the exponential for the remdesivir group in ACTT-1. The first column in Table 7 below assumes the Placebo arm in this study will have almost identical recovery experience as the remdesivir arm in ACTT-1. The second and the third column (median time to recovery of 6 and 5 days, respectively) assume improved recovery rate in our Placebo arm (0.882 and 0.913 versus 0.851) when factoring in corticosteroid use and evolving SOC in general. The sample size required for risk ratios ranging from 1.35-1.5, is shown in Table 7. and suggests a sample size of approximately 350 participants will have 80% power to detect a risk ratio of 1.37.

Table 7 shows the sample size needed to have 80% power with type I error rate of 0.05 to detect various RR for differing values of median days to recovery in the SOC+placebo arm. The entries in the cells show the sample size needed along with expected 28-day recovery rates in the placebo vs. IC14 arms.

Table 7. Sample Size Calculations			
	Standard of Care Group: Median Days to Recovery		
Effect (RR)	7	6	5
1.35	392 ^a 0.851 / 0.924 ^b	382 0.882 / 0.944	372 0.913 / 0.963
	312 0.851 / 0.931	302 0.882 / 0.950	296 0.913 / 0.967
1.40	254 0.851 / 0.937	248 0.882 / 0.955	242 0.913 / 0.971
	212 0.851 / 0.943	208 0.882 / 0.959	202 0.913 / 0.974

a. Sample size (n) b. Recovery rate (placebo arm / IC14 arm)

Based on available data regarding current standard of care with remdesivir and/or dexamethasone, sample size calculations for this study are based on a median time to recovery of 6 days in the Placebo arm and a RR ratio of 1.4. Under this scenario, enrollment of 302 study participants would be expected in order to observe 278 recoveries. Because the recovery rate in the placebo arm and the RR may vary, anticipated enrollment will be between 302-350 participants to observe at least 278 recoveries. If at least 278 recoveries are observed after 302 participants have completed the study, enrollment will stop. Otherwise enrollment will continue until 278 recoveries are observed or the maximum enrollment of 350 participants is reached. Because this study will be conducted in hospitalized patients, the dropout rate is not expected to affect these sample size assumptions in a significant manner.

14. Identification and Access to Source Data

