8.1. Enrollment

The research study will be explained in lay terms to each potential research participant. The potential participant or, in the instance that the patient is not able to sign for themselves, a Legally Authorized Representative (LAR) will sign an

electronic informed consent form before undergoing any study procedures. Once the electronic informed consent has been signed, the participant is considered to be enrolled in the study and will be assigned a unique participant number.

Participants will be enrolled at approximately 14 sites in the United States. Enrollment will occur over a period of 6 to 12 months until approximately 300 participants are enrolled, randomized and treated with the first dose of the study drug. If necessary, enrollment and treatment may continue for up to 350 participants. It is anticipated that enrollment will begin in Q1 2021.

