11.1. Participant Completion

The study will be complete for each participant at the end of the Day 60 visit.

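### Does the 80% power quoted for a rate ratio of 1.37 with 350 participants misstate the power of the 278-recovery enrolment rule?

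*Combined protocol and SAP*

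**What the plan says.** Section 13.11 (Sample Size Calculations) first surveys effects. Table 7 lists the total size needed for "80% power with type I error rate of 0.05 to detect various RR" at placebo medians of 7, 6 and 5 days. The text above the table says that it "suggests a sample size of approximately 350 participants will have 80% power to detect a risk ratio of 1.37".

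The section then fixes the design: placebo median 6 days, rate ratio 1.4, 302 participants expected to yield 278 recoveries. The enrolment rule is: "If at least 278 recoveries are observed after 302 participants have completed the study, enrollment will stop". It goes on: "Otherwise enrollment will continue until 278 recoveries are observed or the maximum enrollment of 350 participants is reached".

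Section 8.1 (Enrollment) is consistent with a target and a ceiling: "Enrollment will occur over a period of 6 to 12 months until approximately 300 participants are enrolled, randomized and treated", followed by "If necessary, enrollment and treatment may continue for up to 350 participants".

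Two sections bear on when a participant counts as having completed. Section 11.1 says: "The study will be complete for each participant at the end of the Day 60 visit". Section 13.9.1 (Interim Analyses) uses a shorter clock for its looks: "When 150 study participants have completed the 28-day study period".

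No section says whether recruitment pauses between the 302nd enrolment and the count. The only enrolment halt described is the one for ad hoc safety review in section 12.7.3.2.

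**The concern.** Two detectable effects, 1.37 and 1.40, stand in adjacent paragraphs, and a quick reader may take both as properties of one trial. They are not. The rule aims at 278 recoveries, and 80% power at 1.37 needs 317. If recruitment is held at 302 until the outcomes are in, the trial ends at around 278 recoveries and never approaches 350, so the 80% at 1.37 is out of reach.

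The extension is also not a remote branch. At the plan's own design values, 302 participants yield slightly fewer than 278 recoveries on average, so the trial team will quite likely have to apply the continuation clause. The plan does not say whether enrolment is open at that moment, or whether the count is taken at Day 28 or Day 60. If the figure were simply wrong, or if the open point could pull the trial below its planned power, the sample-size section would need correcting.

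**Working it through.** **Inputs, all from the protocol.** Weibull recovery times with shape 0.73; placebo medians of 5, 6 and 7 days; type I error 0.05 and 80% power (13.11); 1:1 allocation (13.1); endpoint through Day 28 (13.2.1). Sidedness is not stated. Two-sided is inferred because it reproduces the 278, while one-sided gives 219.

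**1. Reproduce the plan's event target.** Schoenfeld: d = 4(1.960 + 0.842)² / ln(RR)².

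- RR 1.40: 277.3, rounded up to 278. This matches the plan.
- RR 1.37: 316.8, so 317.
- RR 1.35: 348.6, so 349.

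**2. Reproduce the recovery rates and the design size.** The placebo proportion not recovered at Day 28 is 2^−(28/median)^0.73, and on IC14 it is that value raised to the power RR. At median 6 and RR 1.40 the recovery rates are 0.882 and 0.950, as in Table 7. The mean rate is 0.9156, and 278 / 0.9156 = 303.6, against 302 in the plan. The difference is rounding.

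**3. Check the 350 and 1.37 statement as written.** Power = Φ(ln(RR)·√d / 2 − 1.96), with d the recoveries expected among 350.

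| Placebo median | Recoveries among 350 at RR 1.37 | Power |
|---|---|---|
| 5 days | 328.5 | 81.4% |
| 6 days | 319.9 | 80.4% |
| 7 days | 311.2 | 79.3% |

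The size needed for 80% at RR 1.37 and median 6 is 348. The stated figure is right for 350 enrolled.

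**4. Power at 278 recoveries.**

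- RR 1.40: 80.1%
- RR 1.37: 74.7%
- RR 1.35: 70.6%

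**5. How often 302 is enough.** Total recoveries are the sum of two binomials of 151 each. At median 6 and RR 1.40 the mean is 302 × 0.9156 = 276.5, and the chance of at least 278 is 43%. It is 93% at median 5 and about 5% at median 7. At median 6 the average shortfall is 1.5 recoveries.

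**6. The two ways to fill the gap, at RR 1.37 (log-rank simulation, medians 5 to 7).**

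| Handling at 302 | Mean final size | Power at RR 1.37 |
|---|---|---|
| Held, outcomes known one by one after reopening | 302 to 313 | 74% to 75% |
| Held, then 25 to 50 per month after reopening | 302 to 321 | 74% to 76% |
| Not held, count at Day 28 | 325 to 346 | 76% to 81% |
| Not held, count at Day 60 | 348 to 350 | 79% to 81% |

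Accrual of 25 to 50 per month is an assumption: 300 participants over the 12 or 6 months in section 8.1. The synopsis gives about 6 months of recruitment, which points to the faster rate. At 50 per month without a hold, power is 79% to 81% under either count.

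**7. The same question at the design value, RR 1.40.** Held at 302, simulated power is 80% to 81% across the three medians. With all 350 enrolled, the formula in step 3 gives 86.2%, 85.4% and 84.4% for medians of 5, 6 and 7 days. No reading brings the trial materially below the planned 80%.

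**8. Futility look.** At RR 1.37 it stops about 3% to 4% of trials and costs at most about one point of power.

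**The case for a change.** The strongest case for a change is that the final size, anywhere from about 302 to 350, turns on a choice that nobody has written down. That choice would be made late in the trial, after the futility look at 150, by a coordinating centre that holds unblinded data. A reader of 13.11 is also not told that the 1.37 figure belongs to full enrolment and not to the rule that follows it. Two sentences would settle both points at no cost in participants.

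The factual part stands: the hold is unstated, the completion day can be read as Day 28 or Day 60, and the extension clause is more likely than not to come into play at median 6.

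The inference from it does not. The sentence about 1.37 names 350 participants and rests on a table of fixed sizes. Nothing in the plan claims 80% power at 1.37 for the 278-recovery rule. The next paragraph names 1.4 as the basis of the design and calls 350 a maximum, so the two effects are already told apart. The 75% figure needs a hold that the plan does not state. With enrolment left open and completion at Day 60, the result is 79% to 81%, which is the quoted figure. As for discretion, the range is bounded at both ends in advance, and the trigger as written is a count of recoveries, not an estimate of the treatment difference.

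**Conclusion.** No change follows. The 80% at a rate ratio of 1.37 is a correct statement about 350 enrolled participants, and the 278-recovery rule delivers the planned 80% at its own design value of 1.40.

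What is left is an operating detail: whether recruitment pauses at 302, and on which day the count is made. A trial team can fill this either way without harm. Pausing costs time and gives about 74% to 76% power at 1.37. Not pausing enrols more people within the stated ceiling and gives about 76% to 81%. The spread is at most about 7 points, at an effect the trial was not sized for. At the design value, power is about 80% if recruitment is held and up to 84% to 86% if all 350 enrol. The stratified log-rank test and the recovery target are the same in every case.

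This rests on a two-sided 5% test, the plan's Weibull model with no dropout, and, for the scenarios without a hold, assumed accrual of 25 to 50 per month.

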14.1. Source Data

Source documents and source data are considered to be the original documentation where patient information, visits consultations, examinations and other information are recorded. Documentation of source data is necessary for the reconstruction, evaluation and validation of clinical findings, observations and other activities during a clinical trial. The Source Documents for this study will consist of the records collected by the study team (e.g. eCRFs, etc.). Some of this information may be collected from the participant's medical record.

14.2. Access to Source Data

The site investigators and site staff will make all source data available to the DAIT/NIAID, as well as to relevant health authorities noted above and to the staff of Implicit Biosciences, Ltd. if requested, all of whom are bound to maintain the strict confidentiality of medical and research information that may be linked to identified individuals.

15. Quality Assurance and Quality Control

Each clinical site will perform internal quality management of study conduct, data and biological specimen collection, documentation and completion. An individualized quality management plan will be developed to describe a site's quality management.

Quality control (QC) procedures will be implemented beginning with the data entry system and data QC checks that will be run on the database will be generated. Any missing data or data anomalies will be communicated to the site(s) for clarification/resolution. Study personnel at the Vanderbilt Clinical Coordinating Center and the PPD research organization will review and monitor participant data for quality control purposes.

Following written Standard Operating Procedures (SOPs), the monitors will verify that the clinical trial is conducted and data are generated and biological specimens are collected, documented (recorded), and reported in compliance with the protocol, International Conference on Harmonisation Good Clinical Practice (ICH GCP), and applicable regulatory requirements (e.g., Good Laboratory Practices (GLP), Good Manufacturing Practices (GMP)).

The investigational site will provide direct access to all trial related sites, source data/documents, and reports for the purpose of monitoring and auditing by the sponsor, and inspection by local and regulatory authorities.

16. Protocol Deviations

16.1. Protocol Deviation Definitions

Protocol Deviation – The investigators and site staff will conduct the study in accordance to the protocol; no deviations from the protocol are permitted. Any change, divergence, or departure from the study design or procedures constitutes a protocol deviation. As a result of any deviation, corrective actions will be developed by the site and implemented promptly.

16.1.1. Major Protocol Deviation (Protocol Violation)

A Protocol Violation is a deviation from the IRB approved protocol that may affect the study participant's rights, safety, or well-being and/or the completeness, accuracy and reliability of the study data. In addition, protocol violations include willful or knowing breaches of human subject protection regulations, or policies, any action that is inconsistent with the NIH Human Research Protection Program's research, medical, and ethical principles, and a serious or continuing noncompliance with federal, state, local or institutional human subject protection regulations, policies, or procedures.

16.1.2. Non-Major Protocol Deviation

A non-major protocol deviation is any change, divergence, or departure from the study design or procedures of a research protocol that does not have a major effect on the study participant's rights, safety or well-being, or the completeness, accuracy and reliability of the study data.

16.2. Reporting and Managing Protocol Deviations

The study site principal investigator has the responsibility to identify, document and report protocol deviations as directed by the study Sponsor. However, protocol deviations may also be identified during site monitoring visits or during other forms of study conduct review.

Upon determination that a protocol deviation (major or minor) has occurred, the study staff will; a) notify the site Principal Investigator, and b) will complete an eCRF Protocol Deviation form. The Protocol Deviation form will document, at a minimum, the date the protocol deviation (PD) occurred, the date PD identified, a description of event, whether the deviation resulted in SAE/AE, the signature of PI, a report to the SIRB, and documentation of a corrective action plan.

The VCC, the VCC MM and the IND sponsor (DAIT/NIAID) may request a discussion with the PI to determine the effect of the protocol deviation on the study participant and his/her further study participation, the effect of the protocol deviation on the overall study, and corrective actions. The PI will review and verify the Protocol Deviation form and the VCC will submit to the SIRB, per SIRB regulations. Major protocol deviations will be reviewed by the DSMB. The decision as to whether the Deviation is major or not will be determined by the VCC MM and the IND sponsor (DAIT/ NIAID)

17. Ethical Considerations and Compliance with Good Clinical Practice

17.1. Statement of Compliance

This clinical study will be conducted using good clinical practice (GCP), as delineated in *Guidance for Industry: E6 Good Clinical Practice Consolidated Guidance*, and according to the criteria specified in this study protocol. Before study initiation, the protocol and the informed consent documents will be reviewed and approved by the University of Washington Central IRB and the local institutional IRB at each Study Site. Any amendments to the protocol or to the consent materials will also be approved by the University of Washington Central IRB before they are implemented.

17.2. Informed Consent Process

The consent process will provide information about the study to a prospective participant and will allow adequate time for review and discussion prior to his/her decision. The principal investigator or designee listed on the FDA 1572 will review the consent and answer questions. The consent designee must be listed on the delegation log and have knowledge of the study. The prospective participant will be told that being in the trial is voluntary and that he or she may withdraw from the study at any time, for any reason. All participants (or their legally acceptable representative) will read, sign, and date a consent form before undergoing any study procedures. Consent materials will be presented in participants' primary language. Informed consent may be obtained using paper or electronic procedures, and must comply with relevant regulations and guidance for obtaining consent for COVID-19 studies and the approved use of electronic consent: <https://www.fda.gov/media/116850/download>

The consent process will be ongoing. The consent form will be revised when important new safety information is available, the protocol is amended, and/or new information becomes available that may affect participation in the study.

Appendix A: Sequential Organ Failure Assessment (SOFA) Score

Appendix B: Glasgow Coma Scale (GCS)

Appendix C. Eight-Point Ordinal Scale

Appendix D. EQ5D Instrument

Appendix E. Child Pugh Score

Appendix A: Sequential Organ Failure Assessment (SOFA)

Record the worst value in the previous 24 hours:

PaO_2 mm Hg

FiO_2^* %

Respiratory system

PaO₂/FiO₂ [mmHg (kPa)]	SOFA Score
Greater than or equal to 400 (53.3)	0
Less than 400 (53.3)	+1
Less than 300 (40.0)	+2
Less than 200 (26.7) and mechanically ventilated	+3
Less than 100 (13.3) and mechanically ventilated	+4

Nervous system (See appendix D)

Glasgow coma scale	SOFA Score
15	0
13-14	+1
10-12	+2
6-9	+3
Less than 6	+4

Cardiovascular system

Mean arterial pressure OR administration of vasoactive agents required (Listed doses are in units of mcg/kg/min)	SOFA Score
No hypotension	0
MAP less than 70 mmHg	+1
DOPamine less than or equal to 5 or DOBUTamine (any dose)	+2
DOPamine greater than 5, EPINEPHrine less than or equal to 0.1, or norEPINEPHrine less than or equal to 0.1	+3
DOPamine greater than 15, EPINEPHrine greater than 0.1, or norEPINEPHrine greater than 0.1	+4

Liver

Bilirubin, mg/dL ($\mu\text{mol/L}$)	SOFA Score
1.2 - 1.9 (20-32)	+1
2.0 - 5.9 (33-101)	+2
6.0 – 11.9 (102-204)	+3
Greater than or equal to 12.0	+4

Coagulation

Platelets, $\times 10^3/\mu\text{L}$	SOFA Score
Greater than or equal to 150	0
100-149	+1
50-99	+2
20-49	+3
Less than 20	+4

Kidneys

Creatinine, mg/dL ($\mu\text{mol/L}$) (or urine output, UOP)	SOFA Score
Less than 1.2 (less than 110)	0
1.2 - 1.9 (110-170)	+1

2.0 - 3.4 (171-299)	+2
3.5 - 4.9 (300-440) or UOP less than 500 mL per day	+3
Greater than or equal to 5.0 (greater than 440) or UOP less than 200 mL per day	+4

*Estimating FiO_2 from oxygen flow/delivery rates:

Type of O_2 delivery	Flow rates, L/min	FiO_2
Nasal Cannula		~4% FiO_2 added above room air** per 1 L/min
	Room Air	21%
	1 liter per minute	25%
	2 liters per minute	29%
	3 liters per minute	33%
	4 liters per minute	37%
	5 liters per minute	41%
	6 liters per minute	45%
Simple face mask	~6-12 liters per minute	35-60%**
Non-rebreather mask	10-15 liters per minute	~70-90%
High-flow nasal cannula	Up to 60 liters per minute	30-100%

**Varies based on respiratory rate and minute ventilation.

Even though it is calculated sequentially based on the worst values in the past 24 hours, the SOFA Score is not meant to indicate the success or failure of interventions or to influence medical management.

